1.3 SCHEDULE OF EVENTS

	Screen/ Enroll	Year 1							Year 2 (Week)				Survival Follow Up
		Day		Week									
Procedures	≤28 days Day 1	Day 1	Day 8 ^c	3 ^c	13 ^d	26 ^e	39 ^e	52 ^e	65 ^e	78 ^e	91 ^e	104 ^e	Termination ^j
Informed Consent/Review Eligibility	X												
Medical History	X												
MRI Brain	X			X	X	X	X	X	X	X	X	X	X
QOL Assessments ^b		X		X	X	X	X	X	X	X	X	X	X
Clinic Visit (complete physical exam)	X	X	X	X	X	X	X	X	X	X	X	X	X
ECOG Performance Status	X	X	X	X	X	X	X	X	X	X	X	X	X
Pregnancy Test (WOCBP only) ^g	X												
Concomitant Meds (including corticosteroids agent and dose)	X	X	X	X	X	X	X	X	X	X	X	X	X
Adverse Events ^h	X	X	X	X	X	X	X	X	X	X	X	X	X
Labs (CBC, CMP, CPK, Lipase, Amylase)	X	X	X	X	X	X	X	X	X	X	X	X	X
Research Blood for cfDNA	X												X
RECIST 1.1/RANO-BM	X			X	X	X	X	X	X	X	X	X	X
Systemic Imaging (CT C/A±P or PET/CT)	X ⁱ			X	X	X	X	X	X	X	X	X	X
Brigatinib Administration ^a		X	X	X	X	X	X	X	X	X	X	X	
CNS Radiation for Brain Metastases Progression (as indicated per PI/Sub-I)													X ⁱ
Vitals Collection (BP, spO ₂ and HR)	X	X	X	X	X	X	X	X	X	X	X	X	X
Survival and Disease Status, Current Therapy													X

3-month intervals are defined as 13 weeks (52 weeks per 12 months / 4)

^a All patients will be started on brigatinib 90 mg daily for 7 days, before escalating to 180 mg daily thereafter as tolerated

^b EORTC QLQ-C30 and BN20 brain-specific questionnaire

^c Day 8 and Week 3 procedures have a window of \pm 4 days from Day 1

^d Week 13 procedures have a window of \pm 7 days

^e All time points 26 weeks and onwards inclusive have a window of \pm 14 days

^f For patients removed from study treatment prior to 24 months (Week 104), survival follow-up will be done every 6 months (\pm 14 days from Termination Visit) for up to 24 months from Day 1, or until death or patient withdrawal of consent; this includes for patients who develop CNS progression while on study

^g Pregnancy Test (for WOCBP only) should also be performed prior to any radiation therapy subsequent to enrollment including radiation for brain or extracranial disease according to SOC.

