^h Baseline neurologic symptoms should be scored per Cox, James D., et al "Toxicity criteria of the radiation therapy oncology group (RTOG) and the European organization for research and treatment of cancer (EORTC)." *International Journal of Radiation Oncology• Biology• Physics* 31.5 (1995): 1341-1346. Only patients with neurologic symptoms from their brain metastases that are grade 0, 1, 2 are eligible for inclusion; patients with grade 3 and 4 neurologic symptoms are excluded (see section 5). Scale: Grade 0 (no neurologic symptoms), Grade 1 (Fully functional status (i.e., able to work) with minor neurological findings, no medication needed), Grade 2 (Neurological findings present sufficient to require home care/nursing assistance may be required/medications including steroids/antiseizure agents may be required), Grade 3 (Neurological findings requiring hospitalization for initial management), Grade 4 (Serious neurological impairment that includes paralysis, coma, or seizures > 3 per week despite medication/hospitalization required)

ⁱCNS salvage radiation therapy will be done in the event of brain metastases progression, per treating investigator

^jFor patients discontinuing study treatment prior to Week 104, termination visit assessments (other than CNS salvage therapy, if required) are to occur within 30 days of last dose of study drug. If patient continues on study treatment until Week 104, the study termination visit is to occur at Week 104 (month 24) and patients may transition to SOC brigatinib at that time, if still receiving clinical benefit.

^k Baseline systemic imaging (CT or PET/CT only) performed per standard of care within 6 weeks (42 days) of Day 1 will be permitted

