4. To evaluate the time until the administration of WBRT with brigatinib alone	4. Time until the administration of whole brain-radiotherapy (WBRT) and rates at follow up intervals (up to 24 months from Day 1).	It is important to characterize the time until WBRT with a strategy brigatinib alone, as WBRT is associated with known toxicities.
5. To evaluate longitudinal changes in quality of life with brigatinib alone	5. Quality of life will be assessed using standardized QOL metrics (EORTC QLQ C30/BN 20)	It is important to characterize the longitudinal QOL achieved with a strategy of brigatinib alone.
Exploratory		
1. Analysis of blood at baseline and at progression to correlate with clinical outcomes.	1. Evaluation of cfDNA and/or other blood-based markers at baseline and progression to correlate with clinical outcomes including disease recurrence, survival, and quality of life	Evaluations of cfDNA can offer important insights into prognostic and predictive biomarkers for patients with metastatic ALK+ NSCLC with brain metastases.
2. To characterize corticosteroids	2. Quantification of the agent and dosage of corticosteroids at each study assessment	It is important to quantify the effect of brigatinib on corticosteroid requirements

administration before and after brigatinib initiation		because corticosteroids can be associated with symptoms and negative effects on quality of life
---	--	---

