4 STUDY DESIGN

4.1 OVERALL DESIGN

This is a single arm phase-II study including patients with ALK+ NSCLC and brain metastases, who are either neurologically asymptomatic or have only mild neurologic symptoms (RTOG acute neurologic morbidity score 0-2) from their brain metastases, who are TKI naïve or have had prior exposure to crizotinib, but who are naïve to brigatinib and other ALK TKIs including alectinib, lorlatinib, and ceritinib. At screening and enrollment, patients will have a history and physical exam, CTCAE symptoms assessment, and brief QOL questionnaires.

At day 1, all patients will be started on brigatinib 90 mg daily for 7 days, before escalating to 180 mg daily thereafter as tolerated.

At day 8, patients will be seen for a scheduled clinic visit. Each clinic visit will include toxicity assessment and physical exam. Day 8 procedures have an allowable window of ± 4 days. Brief QOL questionnaires will be administered at baseline (Day 1), at 3 weeks (Day 21), and at 3 months (week 13) and subsequent visits every 3 months.

At 3 weeks (Day 21), patients will be seen for scheduled clinic visits and a scheduled surveillance brain MRI. Week 3 procedures have an allowable window of ± 4 days. Subsequently, patients will have scheduled clinic visits and surveillance brain MRIs at 3 months post enrollment (week 13) and at 3 month intervals for year 1 and 2 (ie, at week 26, 39, 52, 65, 78, 104).

Patients who develop CNS progression during the study will be offered palliative radiation for their brain metastases and their disease status will be recorded as CNS progression event.

Patients who experience disease progression per RECIST 1.1 or RANO BM may continue to be treated with brigatinib if, in the opinion of the treating investigator, they continue to experience clinical benefit. Note, this is an accepted treatment strategy per the contemporary NCCN NSCLC guidelines. In this case, patients will be removed from study treatment and will be followed for survival for up to 24 months from Day 1, but may continue to receive brigatinib per standard of care.

If patients do not experience disease progression, they will complete the study treatment at 24 months. Patients continuing to benefit from brigatinib in the opinion of the treating physician may remain on the drug after 24 months per standard of care.

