8.1.2 EXTRACRANIAL SURVEILLANCE

Patients will have surveillance imaging of the body at 3 months (13 weeks \pm 7 days) and then every 3 months (\pm 14 days) for 2 years or as required for standard of care by the investigator. At the discretion of the investigator, the patient may have a computed tomography (CT) scan of the chest/abdomen, with or without the pelvis OR a positron emission tomography-computed tomography (PET/CT) scan. Extracranial disease status will be graded per standard RECIST 1.1 criteria (Eisenhauer et al. "New response evaluation criteria in solid tumours: revised RECIST guideline (version 1.1)." *European journal of cancer* 45.2 (2009): 228-247.)

8.1.3 QUALITY OF LIFE (QOL) ASSESSMENTS.

QOL will be assessed using the EORTC QLQ-C30 and BN20 brain-specific questionnaire. The EORTC QLQ-C30 is one of the most frequently used questionnaires in cancer patients, and the BN20 is a supplemental questionnaire specifically developed for use with the QLQ-C30 in patients with brain cancer. Both tools have robust psychometric properties resulting from rigorous testing, development, and external validity, and have been used in numerous of oncology trials (Efficace 2002). Specific to PCI, the QLQ-C30 and BN20 have been used in the RTOG PCI trials (RTOG 0212 and 0214) (Gondi 2013), the EORTC 08993-22993 PCI trial (Slotman 2007), and the Intergroup PCI trial (Le Pechoux 2011). The questionnaires are translated and validated in over 80 languages. Use of the questionnaires requires no monetary charge in the non-commercial setting. Together, the questionnaires typically take under 5 minutes to complete, and collection is planned at baseline and with each planned clinical surveillance visit (with the exception of Day 8).

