9.4.3 ANALYSIS OF THE SECONDARY ENDPOINT(S)

Secondary endpoints include several time-to-event endpoints: 4 measuring time-to-progression (time-to-CNS PD, time-to-local PD, time-to-distant brain PD, and time until PD at any site), 2 measuring time-to-death (overall and metastases-specific mortality), as well as time-to-administration of WBRT. All time-to-event endpoints will be analyzed using Kaplan-Meier product-limit methods and summarized graphically using Kaplan-Meier survival plots. In

addition, secondary endpoints will be summarized descriptively, including the rates of events, progressive disease, and survival at the follow up intervals (up to 24 months from Day 1). Cumulative rates of best CNS objective response will be described. For QOL, scores from the QLQ-C30 and BN20 will be normalized to 0-100 scales, changes from baseline of ≥ 10 points will be considered clinically meaningful, and cumulative changes at each assessment will be described and time-to-event outcomes for declines in QOL will be summarized graphically using Kaplan-Meier and cumulative incidence plots.

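### Per-visit QOL descriptions rest on a shrinking, healthier group and probably look too favourable; a mixed model on every form would be a cheap but partial remedy

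*Combined protocol and SAP*

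**What the plan says.** Secondary objective 5 in Section 3 is "To evaluate longitudinal changes in quality of life with brigatinib alone". Section 9.4.3 rescales the QLQ-C30 and BN20 to 0-100 and states that "changes from baseline of ≥ 10 points will be considered clinically meaningful". It then plans two things: "cumulative changes at each assessment will be described", and "time-to-event outcomes for declines in QOL will be summarized graphically using Kaplan-Meier and cumulative incidence plots". It gives no longitudinal model, no missing-form rule and no reporting of form completion. Section 9.3 assigns all who start brigatinib to the secondary endpoints on safety, tolerability and duration of therapy or progression, and does not mention QOL.

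Forms are due on Day 1, at week 3, at week 13 and every 13 weeks to week 104 (Sections 1.3 and 8.1.3). Under Section 4.1, when a patient progresses but stays on brigatinib as standard of care, "patients will be removed from study treatment and will be followed for survival for up to 24 months from Day 1". Section 6.5 sends those who change therapy down the same route. The Section 1.3 footnotes say that for early leavers "termination visit assessments (other than CNS salvage therapy, if required) are to occur within 30 days of last dose of study drug", and that after this "survival follow-up will be done every 6 months". The last column of the schedule carries a QOL mark but is headed both as survival follow-up and as termination. Whether any QOL form is due after the termination visit is therefore not clear.

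**The concern.** Leaving is tied to worsening by design. Under the RANO-BM table in Section 8.1.1, worse clinical status alone counts as progression, and Section 7.2 makes intolerable toxicity a reason to stop treatment. Patients whose QOL falls are therefore more likely to stop contributing scheduled forms. For an early leaver, the form most likely to show the fall is the termination form. It generally matches no scheduled week, and Section 9.4.3 does not say how it enters a per-assessment description.

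Any available-case summary at a late visit, whether a mean or the proportion changing by at least 10 points, then describes those who stayed. A real average decline could read as stability. QOL is part of the protocol's argument for deferring brain radiation (Sections 2.1 to 2.3), so an error in the favourable direction would matter when the results are interpreted.

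**Working it through.** The plan gives no sample size, power or precision for QOL, so there is no QOL figure to reproduce. Its only power figure concerns 3-month disease control: success at 16 or more of 19 gives exact one-sided alpha 0.0230 and power 0.8850, which matches the stated 88.5%. Only the planned enrolment of 23 carries over to QOL.

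The QOL inputs below are all assumptions. Bias is the estimate minus the true mean change. The share removed is 1 − (model bias ÷ available-case bias).

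**Set A** (1,500 patients per setting, to show bias). True mean change is −1 point per 13 weeks, slope SD 2, error SD 8. The hazard of leaving per 13 weeks is 0.10 × exp(−g × observed change), with g = 0.03 or 0.06. The model is linear with random intercept and slope.

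| | Week 52 | Week 104 |
|---|---|---|
| True change | −4.0 | −8.0 |
| Per-visit mean | −2.0 to −0.7 | −2.0 to +3.3 |
| Bias of per-visit mean | −2.0 + 4.0 = 2.0, to −0.7 + 4.0 = 3.3 | −2.0 + 8.0 = 6.0, to 3.3 + 8.0 = 11.3 |
| Mixed model, all forms including termination | −3.9 to −4.0 | −7.8 to −7.9 |

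At week 104, 39% to 31% are still observed, which for 23 patients is 23 × 0.39 = 9.0 down to 23 × 0.31 = 7.1. Near-perfect recovery is built into this set: leaving depends on a score that the termination form records, and the fitted model is the one that generated the data. If the leaving form is not completed (baseline SD 12 assumed), the model gives −6.4 to −4.5 at week 104, a bias of 1.6 to 3.5.

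**Set B** (200,000 patients per scenario). Baseline mean 65, between-patient SD 16, residual SD 12, mean slope −10 points over 104 weeks with SD 15, nominal 40% or 60% leaving by week 104. The model is a likelihood repeated-measures model with unstructured covariance. Week-104 results:

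| What drives leaving | Available-case bias | Model bias | Share removed |
|---|---|---|---|
| Previous recorded score | +1.8 to +4.2 | about 0 | 96% to 101% |
| Current score, recorded on a termination form | +1.8 to +4.5 | about 0 | 98% to 101% |
| Current score, never recorded | +2.5 to +6.0 | +1.9 to +6.5 | −8% to 24% |
| 15-point fall at progression, no form afterwards | +6.0 to +9.0 | +6.0 to +9.0 | 0% |
| Same fall, one termination form, QOL stays low | +5.1 to +7.4 | +2.5 to +2.9 | 52% to 61% |

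Examples: 1 − 2.9/7.4 = 0.61; 1 − 1.9/2.5 = 0.24; 1 − 6.5/6.0 = −0.08. At week 52 the last row gives 36% to 39%. In the third row at week 52 the model does worse than the raw mean (bias 1.0 to 3.6 against 0.7 to 2.1).

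Across both sets the available-case bias at week 104 runs from 1.8 to 11.3 points, and its direction is favourable in every scenario.

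**Precision at n = 23.** Four Set A settings were used: both values of g, with and without the leaving form. Week-104 root mean square error was 4.6 to 7.0 for the mixed model and 7.4 to 12.5 for the per-visit mean. The model's 95% interval was about ±9 to ±10 points, and 5% to 9% of fits failed or were singular in a run at this size.

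**The case against.** A reader might infer that QOL is analysed only visit by visit. The documents do not support that: the same sentence plans time-to-decline plots, to which every patient can contribute until decline or censoring, and a fall on the termination form can count as an event. This stands, but it covers only part of the problem. The plots do not estimate mean change, and censoring at treatment exit may be informative. The scale, any need for confirmation, and the handling of death and progression are also not stated.

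A reader might also infer that the plan restricts QOL to patients still on treatment, uses per-visit means, or discards the termination form. None of these is written. The restriction is inferred from the schedule, and no QOL analysis set is given. The description of cumulative changes could mean proportions. For patients treated to week 104, the termination visit is the week-104 visit. Selection affects available-case proportions as well as means, but the sizes above apply to means.

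The strongest objection concerns the remedy. It is tempting to say that a mixed model would largely correct the bias. That follows only if recorded scores explain leaving; no model recovers a fall that no form captured, and a straight line fits a step fall poorly. With 23 patients the interval is wider than the 8-point decline assumed in Set A. This stands in full and limits what the fix may claim.

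Finally, QOL while on brigatinib alone is a defensible target, and QOL is a secondary objective without a hypothesis; the protocol's test of acceptability is 3-month CNS control. This lowers the weight of the point, but the plan should still say what its late summaries represent.

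**Conclusion.** The point holds as a worthwhile improvement to a secondary analysis. The late per-visit descriptions will come from a selected group and probably look too favourable, by about 2 to 11 points at week 104 under the assumed scenarios, against a 10-point threshold. The direction follows from the schedule and the rules for leaving treatment. The size rests wholly on assumed variances, slopes and leaving rates.

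The mixed model is better than the raw description alone, but it is not a cure. In Set B it removed nearly all the bias when recorded scores explained leaving, about half when a lasting fall appeared on one termination form, and between nothing and a quarter when the fall was never recorded. Under Set A's linear assumptions at n = 23 it was closer to the truth than the per-visit mean in all four settings.

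**What to change.** In Section 9.4.3, keep the raw description and the time-to-decline plots, and add:

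- A parsimonious linear mixed model (random intercept and slope, actual assessment date as time) in all patients who start brigatinib, using every QOL form including the termination form. Report change from baseline with 95% confidence intervals at each visit.
- The number of forms expected and received at each visit.
- A statement that the model is valid under missing at random and describes QOL while alive.
- A simple delta-adjusted sensitivity analysis that lowers the unrecorded scores after leaving by a range of fixed amounts, reaching at least the plan's own 10 points.

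It would also help to state in Section 1.3 whether QOL forms are due after the termination visit, since that decides how much the model has to work with.

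The analysis needs a little more work and no new data. The price is wide intervals (about ±9 to ±10 points at week 104 with 23 patients), occasional fitting failures and a missing-data assumption that cannot be tested.

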9.4.4 SAFETY ANALYSES

Safety will be measured via the CTCAE Version 4.03 criteria and the rate and type of adverse event (AE) will be compared to historical controls and assessed for any increased risk. Listings will be produced of all study-related AEs, which will be reviewed by the study PI. Additionally, any serious adverse event (SAE) will be reported within 24 hours to the study PI who will investigate the attribution of the SAE to the experimental treatment and only continue the study if the experimental treatment is considered safe.

9.4.5 BASELINE DESCRIPTIVE STATISTICS

Subject baseline characteristics will be summarized using descriptive statistics. Quantitative variables will be summarized using both measures of the center and spread as well as quantiles of each variable's distribution (e.g. Mean, SD, Minimum, Q_1 , Median, Q_3 , and Maximum). Qualitative variables will be summarized using counts and percentages.

9.4.6 PLANNED INTERIM ANALYSES

This study is designed to enroll approximately 23 patients in order to yield 19 evaluable patients. Given this relatively small sample size, there are no planned interim analyses for efficacy or futility. After 19 evaluable patients have completed a 3-month brain MRI (allowing for analysis of the primary endpoint of DCR of brain metastases at 3 months), an initial analysis of the primary endpoint and short-term data on secondary endpoints may be performed.

9.4.6.1 SUB-GROUP ANALYSES

Subgroup analyses will be conducted as necessary in order to inform the sensible design of follow-up studies to this trial. The purpose of such subgroup analyses will be to investigate

which subgroups demonstrated favorable response rates to the experimental treatment of brigatinib.

9.4.7 TABULATION OF INDIVIDUAL PARTICIPANT DATA

Listings will be created from all study data, grouped by domain (e.g. demographics, adverse events, lab values, outcome data, etc.).

9.4.8 EXPLORATORY ANALYSES

Blood will be collected at baseline and at progression. For exploratory analyses, circulating free (cf) DNA levels and/or other blood-based markers will be correlated with measured study endpoints including overall survival, disease progression, and quality of life.

10 SUPPORTING DOCUMENTATION AND OPERATIONAL CONSIDERATIONS

10.1 REGULATORY, ETHICAL, AND STUDY OVERSIGHT CONSIDERATIONS

10.1.1 INFORMED CONSENT PROCESS

10.1.1.1 CONSENT/ASSENT AND OTHER INFORMATIONAL DOCUMENTS PROVIDED TO PARTICIPANTS

Consent forms describing in detail the study agent, study procedures, and risks are given to the participant and written documentation of informed consent is required prior to starting intervention/administering study product.

10.1.1.2 CONSENT PROCEDURES AND DOCUMENTATION

Informed consent process will be initiated prior to the individual's agreeing to participate in the study and continues throughout the individual's study participation. Extensive discussion of risks and possible benefits of participation will be provided to the participants and their families.

Consent forms will be IRB-approved and the participant will be asked to read and review the document. The investigator will explain the research study to the participant and answer any questions that may arise. All participants will receive a verbal explanation in terms suited to their

comprehension of the purposes, procedures, and potential risks of the study and of their rights as research participants. Participants will have the opportunity to carefully review the written consent form and ask questions prior to signing. The participants will have the opportunity to discuss the study with their surrogates or think about it prior to agreeing to participate. The participant will sign the informed consent document prior to any procedures being done specifically for the study.

The participants may withdraw consent at any time throughout the course of the trial. A copy of the informed consent document will be given to the participants for their records. The rights and welfare of the participants will be protected by emphasizing to them that the quality of their medical care will not be adversely affected if they decline to participate in this study.

